6.4.4.2 Multivariate display of immunogenicity endpoints

Data visualization techniques may be used to explore the relationship among immunogenicity readouts. The set of readouts may be based on one of the primary endpoints (eg, ICS), on the set of primary endpoints, or on immunogenicity endpoints that also include secondary or exploratory endpoints. To understand the relationship between pairs of readouts, scatter plots may be used when the number of readouts is small or for a larger number of readouts, a heat map showing the degree of correlation between any two pairs. Principal component analysis (PCA) and associated ‘biplots’ of the scores and loadings are particularly useful to understand associations between readouts, especially when readouts are correlated (60). PCA is a method to reduce the dimensionality of the number of readouts to a smaller set of values (principal components) that are normalized linear combinations of the readouts in such a way that the first principal component accounts for the most variability in the data and subsequent components, while maximizing variability, are uncorrelated with each other. A ‘biplot’ displays the first and second principal component scores and principal component loadings. The x-axis is the value from the first principal component and the y-axis is the second principal component, where each axis label includes the percentage of variation in the total set of readouts captured by the principal component. The top axis is the first principal component loadings and the right axis is the second principal component loadings. An arrow is drawn for each immunogenicity readout (eg, Env-specific CD4+ T cell polyfunctionality score, Env-specific CD8+ T cell total magnitude) from the origin to the point defined by its first two principal component loadings. The length of the arrow represents the amount of total variation of the set of readouts captured by the given readout. The direction of an arrow conveys the extent to which the variation of a readout is in the direction of the first or second principal component. The angle between two arrows conveys information about the correlation of the two readouts, with a zero degree angle denoting perfect correlation and a 90 degree angle denoting no correlation. Each arrow on the biplot is labeled by the immunogenicity readout it represents. A biplot is annotated with key meta-information such as the treatment arm (most common application) or a demographic category. Depending on the application, K-means clustering and hierarchical clustering may also be applied for multivariate graphical display of immunogenicity readouts.

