6.1.1 Sample size calculations for safety

The goal of the safety evaluation for this study is to identify safety concerns associated with product administration. The ability of the study to detect serious adverse events (SAEs) (see Section 11) can be expressed by the true event rate above which at least 1 SAE would likely be observed and the true event rate below which no events would likely be observed. Specifically, for the vaccine arm ($n = 10$) in Part A, there is a 90% chance of observing at least 1 event if the true rate of such an event is 20.6% or more; and there is a 90% chance of observing no events if the true rate is 1% or less. For each vaccine arm ($n = 21$) in

Part B, there is a 90% chance of observing at least 1 event if the true rate of such an event is 10.4% or more; and there is a 90% chance of observing no events if the true rate is 0.5% or less. For the vaccine arms combined from Part B (n=42), there is a 90% chance of observing at least 1 event if the true rate of such an event is 5.4% or more; and there is a 90% chance of observing no events if the true rate is 0.2% or less. As a reference, in HVTN vaccine trials from December 2000 through April 2014, about 4% of participants who received placebos experienced an SAE.

Binomial probabilities of observing 0, 1 or more, and 2 or more events for the arm of size 10 in Part A, an arm of size 21 in Part B, and for the combined vaccine arms in Part B of size 42 are presented in [Table 6-1](#) for a range of possible true adverse event rates. These calculations provide a more complete picture of the sensitivity of this study design to identify potential safety problems with the vaccine.

Table 6-1 Probability of observing 0, 1 or more, and 2 or more events, for an arm (or combined arms) of size n=10, 21, and 42, for a range of possible adverse event rates

True event rate (%)	Pr(0/10)	Pr(1+/10)	Pr(2+/10)	Pr(0/21)	Pr(1+/21)	Pr(2+/21)	Pr(0/42)	Pr(1+/42)	Pr(2+/42)
1	90.4	9.6	0.4	81	19	1.9	65.6	34.4	6.6
4	66.5	33.5	5.8	42.4	57.6	20.4	18	82	50.5
10	34.9	65.1	26.4	10.9	89.1	63.5	1.2	98.8	93.2
20	10.7	89.3	62.4	0.9	99.1	94.2	<0.001	>99.9	99.9
30	2.8	97.2	85.1	0.1	99.9	99.4	<0.001	>99.9	>99.9
40	0.6	99.4	95.4	<0.001	>99.9	>99.9	<0.001	>99.9	>99.9

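### Protocol 6.4.4.2 reads biplot angles as correlations, which does not hold for arrows drawn as the text describes: the scaling is unsettled, and two components may not be enough

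*Protocol*

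**What the plan says.** Protocol 6.4.4.2 presents the biplot as one optional tool: "Data visualization techniques may be used to explore the relationship among immunogenicity readouts". For pairwise relationships it offers scatter plots when there are few readouts and, when there are more, "a heat map showing the degree of correlation between any two pairs".

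Its description of the biplot has four elements that bear on this point:

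- Components are "normalized linear combinations of the readouts in such a way that the first principal component accounts for the most variability".
- Each arrow runs "from the origin to the point defined by its first two principal component loadings".
- On length: "The length of the arrow represents the amount of total variation of the set of readouts captured by the given readout".
- On angle, the reading rule ends "with a zero degree angle denoting perfect correlation and a 90 degree angle denoting no correlation".

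Only two components are shown, and each axis label is to carry its percentage of variation. The section does not say whether loadings are multiplied by the square root of the eigenvalue, and it sets no condition on the variance captured. SAP section 10, which lists the immunogenicity tables and figures by assay, contains no principal component analysis or biplot.

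**The concern.** The angle between two arrows depends on how the loadings are scaled and on how much of each readout lies in the plotted plane. The reading rule mentions neither, yet it gives exact meanings to 0 and 90 degrees. The section's other statements point two ways: the definition of the components suggests unit-length loadings, while the length sentence fits eigenvalue-scaled loadings better. A programmer cannot tell which to plot, and the rule is not generally right under either.

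At stake is the purpose of the display, which is to show which readouts move together. If a figure is made and captioned with this rule, correlated assays could be described as unrelated, or unrelated ones as close to each other.

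**Working it through.** **Inputs.** The construction and reading rule are from Protocol 6.4.4.2. The 18 evaluable participants per Part B vaccine arm are from Protocol 6.1.2, so n = 2 × 18 = 36. The documents do not give the number of readouts or their correlations. I assumed 12 readouts, so 12 × 11 / 2 = 66 pairs, and three correlation patterns.

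**Formulas.** Let the correlation matrix have eigenvalues λk and unit-length eigenvectors with entries v(i,k). Then r(i,j) = Σk λk v(i,k) v(j,k), summed over all components.

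- Unscaled arrow for readout i: (v(i,1), v(i,2)). The dot product of two arrows leaves out the λ weights, so the angle is not tied to r.
- Scaled arrow: (√λ1 v(i,1), √λ2 v(i,2)). The dot product is the first two terms of r(i,j), and the squared length is the share of readout i's variance in the plane. The cosine equals r exactly when two components carry all the variance of both readouts, and only approximately otherwise.

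**Problem 1, scaling: exact example.** Take 12 readouts in two blocks of six, with r = 0.8 within and 0.5 between blocks.

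- λ1 = 1 + 5(0.8) + 6(0.5) = 8 and λ2 = 1 + 5(0.8) − 6(0.5) = 2. The plane holds (8 + 2)/12 = 83% of the variance.
- Every loading is ±1/√12, with the same sign on component 1 and opposite signs between blocks on component 2.
- Unscaled, between-block pair: dot product 1/12 − 1/12 = 0, so 90 degrees. The rule reads this as no correlation, but r = 0.5.
- Scaled, same pair: cosine = (8 − 2)/(8 + 2) = 0.6, so 53 degrees. The angle for r = 0.5 would be 60.

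**Problem 2, truncation: exact example.** Take five readouts. A and B are uncorrelated, each has r = 0.5 with C, and D and E form a separate pair with r = 0.5. The first two eigenvalues are 1.707 and 1.5, so the plane holds 3.207/5 = 64%. A and B both have loadings (0.5, 0) up to sign. They lie at 0 degrees to each other under either scaling, although r = 0.

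**Simulation** (n = 36, 12 readouts, correlation-matrix components; average pairs per dataset out of 66):

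| Pattern | Variance in two components | Pairs counted | Unscaled | Scaled |
|---|---|---|---|---|
| All r = 0.6 | – | within 10° of perpendicular | about 8, median r about 0.54 | about 0.1 |
| Two blocks, 0.8 / 0.5 | 84% | within 10° of perpendicular | about 27, median r about 0.50 | about 0.3 |
| All independent | 32% | within 10° of each other | about 3.2, median r about 0.15 | about 3.3, median r about 0.15 |

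The first two rows show the scaling problem, which rescaling nearly removes. In the block pattern the plane captures most of the variance, so poor capture is not the cause. The third row shows the truncation problem, which rescaling leaves unchanged.

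**The case against.** - **The section does not define the scaling of its loadings.** If scaled loadings were meant, as the length sentence suggests, the first problem almost disappears. This stands in part. It shows that the paragraph mixes conventions, so the scaling must be stated. It does not rescue the exact rule, because the truncation problem remains.
- **The wording is softer than an equation.** The rule opens by saying only that the angle is informative about correlation, and the axis labels show the percentage captured. Both are true. But the same sentence then assigns unqualified meanings to 0 and 90 degrees, and nothing tells the reader to use the percentages.
- **Nothing planned depends on it.** This stands. The one cross-assay correlation the SAP specifies, between the two ADCC assays in section 10.3, uses a correlation with scatter plots and regression lines.

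A reader might also infer more than the documents support:

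- *That unit-length loadings cause both errors.* Unrelated readouts drawn close together come mainly from showing two components. Loading scale alone can do it in constructed cases: with 20 readouts, full capture and a dominant first component, a pair with r = 0 sits at 25.8 degrees unscaled and 90 scaled. In a random search with 3 to 8 readouts and full capture, pairs with absolute r below 0.05 never came closer than 49.8 degrees.
- *That a pair with r = 0.99 would be drawn at 90 degrees.* This is exact for a two-readout biplot with unit-length loadings, but the section assigns scatter plots to small sets of readouts, so that figure is outside the intended use.

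**Conclusion.** The angle rule is wrong as written, with minimal consequence. On the plain reading of the text it can present moderately correlated readouts as unrelated: about 8 or 27 of 66 pairs in the two correlated patterns tried. With scaled arrows the angle is a usable approximation when the plane captures most of both readouts, and exact when it captures all. When it captures little, about 3 of 66 unrelated pairs look nearly parallel under either scaling.

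The algebra needs no assumptions. The counts rest on 12 readouts, 36 evaluable vaccinees and invented correlation patterns, so they show what can happen and do not forecast this trial's data.

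It should not be inferred that any immunogenicity conclusion is at risk. The display is optional and exploratory, is not in the SAP, and no test, ranking or regimen selection uses an angle.

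**What to change.** In Protocol 6.4.4.2, or in the SAP if a biplot is to be produced:

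1. State that arrows are drawn at loadings multiplied by the square root of the eigenvalue, from an analysis of standardized readouts. The arrow-length sentence should then be worded to match.
2. Replace the exact angle rule with a statement that angles approximate correlation only to the extent that the two plotted components capture the variance of both readouts. No fixed cut-off is needed.
3. Take any statement about correlation between readouts from the coefficients, using the heat map or scatter plots the section already names.

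The cost is a plotting option, a few sentences and longer captions. One property is given up: under this scaling, distances between participant points are less directly readable. No endpoint, sample size, test or trial procedure changes.

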
6.4.4.3 Primary analyses of neutralization magnitude-breadth curves

Separate analyses of magnitude-breadth of neutralization will be conducted for the Tier 1B isolate panel and for the Tier 2 isolate panel, for all analyses whether primary, secondary, or exploratory.

For each panel, individual magnitude-breadth curves will be plotted by vaccine arm and pooled placebo, with average magnitude-breadth curves overlaid on the plots. For each panel, the area-under-the-magnitude-breadth curve (AUC-MB) (61) will be computed for each participant, as described in (62). Dunnett’s procedure will be applied with 2-sided alpha = 0.05 to determine which of the two vaccine arms have a significantly higher mean AUC-MB than that of the pooled

placebo groups, as described in (63) (see their formula (1.1)). This procedure will be applied to construct 95% CIs about the 2 differences in mean AUC-MB for each vaccine regimen versus the pooled placebos (vaccine – placebo), which simultaneously have at least 95% coverage probability.

The vaccine regimens will be ranked by the estimated mean of the AUC-MB curves. The vaccine regimen with the highest estimated mean will be selected as the best regimen.

6.4.4.4 Secondary analyses of neutralization magnitude-breadth curves

Superiority comparisons of vaccine regimens

Simultaneous 95% CIs about the mean-differences in AUC-MBs for each vaccine regimen versus pooled placebo will be reported. These CIs are computed as the estimated mean-difference plus or minus $t_{N-2,025}$ multiplied by the square-root of $S_2 (1/n_1 + 1/n_2)$, where $t_{N-2,025}$ is the 97.5th percentile of a t-distribution with $N - 2$ degrees of freedom, where N is the total number of vaccine recipients evaluated (summing over the two vaccine regimens). In addition, S_2 is an estimate of the common sample variance of the AUC-MB, whereas n_1 and n_2 are the sample sizes of evaluable participants for vaccine regimens 1 and 2 being compared. If the 95% CI comparing the two vaccine arms excludes zero then the two vaccine arms have a significant difference bounding the false positive rate at 5%. Nominal (unadjusted) 95% CIs comparing the vaccine arms will also be reported.

Omnibus comparison of magnitude-breadth distributions

The analyses of magnitude-breadth described above are based on the endpoint area-under-the-curve, which is interpreted as the average \log_{10} IC50 to the set of isolates in the test panel. Use of this endpoint is maximally statistically powerful if 1 vaccine arm has greater magnitude and breadth than the comparator vaccine arm, but may miss an effect wherein 1 vaccine arm has greater magnitude and the comparator vaccine arm has greater breadth. Therefore, a secondary analysis may compare the distribution of magnitude-breadth curves among vaccine arms using the test statistic $\max|B_d^G|$ from Huang, et al (62) (see page 85), which is designed to detect general differences in magnitude-breadth curve distributions.

Selecting the best vaccine regimen

The best vaccine regimen will be deemed as that with the greatest value of the $\max|B_d^G|$ test statistic comparing its distribution of magnitude-breadth curves versus the pooled placebo group.

Superiority comparisons of vaccine regimens

Similarly, the $\max|B_d^G|$ test statistic will be used to compare the distribution of magnitude-breadth curves between the two vaccine regimens. Nominal (unadjusted) 95% CIs comparing the two vaccine arms will also be reported.

6.4.4.5 Analyses of IgG binding antibody magnitude and breadth

Secondary objectives 1 and 3 include the analysis of magnitude and breadth of IgG to panels of Env antigens. For each panel of Envs, the same statistical methods described above for assessing magnitude and breadth of neutralization responses will be used.

6.4.4.6 Analysis of CD4+ and CD8+ T-cell response as measured by the ICS assay

The analysis of CD4+ and CD8+ T-cell response rates as measured by the ICS assay will be evaluated and compared as described under the general approach. For each T-cell subset, the positivity call for each peptide pool will include a multiple comparison adjustment for the number of peptide pools used in the assay. In general, the Mixture Models for Single-cell Assays (MIMOSA) statistical framework (64) and/or the Fisher's exact test-based positivity criteria will be used. Details of the positivity criteria will be discussed in the SAP. The magnitude of marginal response will be analyzed as described for quantitative data in the general approach section. For each T-cell subset, graphs will be used to display the background-subtracted magnitudes for each participant by protein, treatment arm and timepoint. When 3 or more cytokines are being measured by the ICS assay, the polyfunctionality of ICS responses may also be analyzed as an exploratory endpoint. Besides descriptive plots of the magnitude of polyfunctional responses, the COMPASS (Combinatorial Polyfunctionality analysis of Antigen-Specific T-cell Subsets) statistical framework (65) may also be used to perform joint modelling of multiple T-cell subsets of different cytokine combinations. For example, the functionality score (FS) and the polyfunctionality score (PFS) may be used to summarize the multi-parameter ICS responses.

6.4.4.7 Analysis of epitope mapping data

The minimal set of optimal length epitopes that can explain the observed T cells responses to a set of individually tested overlapping 15mer peptides may be obtained to assess the breadth and depth of the T cell responses based on the epitope mapping data. When HLA data are also available, computational HLA:peptide binding predictors (eg, NetMHCpan) may be used to more accurately identify each participant's T-cell epitopes.

Once estimates of breadth (number of epitopes) are determined for each participant by the above method or other methods, the distribution of participants with different numbers of total or antigen-specific reactive epitopes may be used to summarize the epitope mapping-based breadth data for each vaccine regimen. Poisson regression models with robust covariance ("sandwich") estimators or other count data analysis methods may be used to compare epitope breadth between vaccine regimens. Zero-inflated models may also be considered if there is interest in differentiating true zero breadth (ie, zero epitope recognized) and excess zeros (ie, no epitope mapping data due to negative T-cell response) in the data.

The set of epitopes may also be used to assess “coverage” of a representative set of circulating viruses by each participant’s set of T-cell responses. The coverage provided by each epitope is defined by the fraction of viruses that match the sequence of the mapped epitope. The coverage provided by a participant’s set of epitopes is defined by the fraction of viruses covered by at least one of the participant’s epitopes.

6.4.4.8 Analysis of multiplexed immunoassay data

When a small panel of analytes (eg, ≤ 5) is being assessed in a multiplexed immunoassay, the analysis of response rates and response magnitudes will be evaluated and compared as described under the general approach. Details for calculating a positive response and response magnitude will be provided in the SAP. When a larger panel is being assessed, two approaches may be considered to evaluate the magnitude and breadth of these responses. First, Magnitude–Breadth (M-B) curves maybe employed to display individual- and group-level response breadth as a function of magnitude. Two choices are to compare the M-B curves among vaccine arms, as follows: a non-parametric Wilcoxon rank sum test on the subject-specific area-under-the M-B curve (AUC M-B) or a Kolmogorov-Smirnov type test on the 2 group-average M-B curves. Simulations can be used to obtain 2-sided p-values for the latter test. Second, a weighted-average score-like variable may be constructed to account for the correlations between analytes as an integrate magnitude of responses to multiple analytes. Similar group comparison methods described in the first approach may be adopted. Details of either approach will be described in the SAP.

6.4.5 Exploratory analyses of binding IgG antibodies including the Month 3.5 and Month 14 timepoints

To assess Exploratory objective 1, for each participant with IgG binding antibody data measured at the Month 3.5, 8.5, and 14 timepoints, the Scaled area-under-the (time) curve will be calculated based on linear segments between Month 0 and 3.5, 3.5 and 8.5, and 8.5 and 14, divided by 14 months. The individual participant IgG curves over time will be plotted stratified by vaccine arm and for the pooled placebo group, together with estimates of the mean at each of the three timepoints with a 95% confidence interval (based on sample averages and a t-statistic based confidence interval). Moreover, a two-sample t-test with unequal variances will be used to test whether the mean Scaled AUC differs between the two vaccine regimens, and correspondingly a t-statistic based 95% confidence interval about the mean vaccine arm difference in Scaled AUC will be reported.

6.4.6 Analyses prior to end of scheduled follow-up visits

Any analyses conducted prior to the end of the scheduled follow-up visits should not compromise the integrity of the trial in terms of participant retention or safety or immunogenicity endpoint assessments. In particular, early unblinded analyses by treatment assignment require careful consideration and should be made available on a need to know basis only.

6.4.6.1 Safety

During the course of the trial, unblinded analyses of safety data will be prepared approximately every 4 months during the main study, as defined in Section 3, for review by the SMB. Ad hoc safety reports may also be prepared for SMB review at the request of the HVTN 124 PSRT. The HVTN leadership must approve any other requests for unblinded safety data prior to the end of the scheduled follow-up visits.

6.4.6.2 Immunogenicity

An unblinded statistical analysis by treatment assignment of a primary immunogenicity endpoint may be performed when all participants have completed the corresponding primary immunogenicity visit and data are available for analysis from at least 80% of these participants. Similarly, an unblinded statistical analysis by treatment assignment of a secondary or exploratory immunogenicity endpoint may be performed when all participants have completed the corresponding immunogenicity visit and data are available for analysis from at least 80% of these participants. However, such analyses for a secondary or exploratory immunogenicity endpoint will only take place after at least one of the primary immunogenicity endpoints of the same class (humoral, cell-mediated, innate or mucosal) or, if no primary endpoint of the same class, at least one of the primary immunogenicity endpoints reaches the aforementioned threshold. The Laboratory Program will review the analysis report prior to distribution to the protocol chairs, DAIDS, vaccine developer, and other key HVTN members and investigators. Distribution of reports will be limited to those with a need to know for the purpose of informing future trial-related decisions. The HVTN leadership must approve any other requests for HVTN immunogenicity analyses prior to the end of the scheduled follow-up visits.

7 Selection and withdrawal of participants

Participants will be healthy, HIV-uninfected (seronegative) adults who comprehend the purpose of the study and have provided written informed consent. Volunteers will be recruited and screened; those determined to be eligible, based on the inclusion and exclusion criteria, will be enrolled in the study. Final eligibility determination will depend on results of laboratory tests, medical history, physical examinations, and answers to self-administered and/or interview questions.

Investigators should always use good clinical judgment in considering a volunteer's overall fitness for trial participation. Some volunteers may not be appropriate for enrollment even if they meet all inclusion/exclusion criteria. Medical, psychiatric, occupational, or other conditions may make evaluation of safety and/or immunogenicity difficult, and some volunteers may be poor candidates for retention.

In the phase 1 clinical trial that tested the polyvalent DNA prime-protein boost DP6-001 HIV vaccine regimen, a high level of reactogenicity was observed, including injection site pain and erythema, fevers, myalgia, fatigue, headache, and arthralgias. There were also AEs of delayed type hypersensitivity (DTH) reactions, and one person each developed Henoch-Schonlein purpura and leukocytoclastic vasculitis. The causes of the DTH reactions and the vasculitis events, and their relationship to each other, if any, are not clear. The next generation regimen has undergone significant changes to further enhance the breadth of nAb responses by carefully selecting optimal gene inserts. Additionally, the adjuvant to be administered with the protein vaccine differs from that in the phase 1 trial of DP6-001. However, as a precaution, the exclusion for autoimmune diseases also excludes people with connective tissue disease, or a history of vasculitis, and urinalysis will be performed as part of the safety evaluation after each vaccination.

Determination of eligibility, taking into account all inclusion and exclusion criteria, must be made within 56 days prior to enrollment unless otherwise noted in Sections [7.1](#) and [7.2](#).

